Recruitment: We will review a register of BMT patients at the CHC who have consented to be contacted about research studies. We will contact patients who meet inclusion criteria and their providers. We will also extract data quarterly from electronic medical records to identify patients who have started buprenorphine treatment within the last 12 weeks. We will not contact patients directly, but instead, we will contact their primary care providers who will inform patients about the study and give the research team permission to contact patients. We will send potential participants letters from their PCP inviting them to participate in the study. Fliers describing the study will be posted at the CHC. The study will be described at staff meetings.

Randomization: A research assistant will contact and meet with eligible patients at the CHC to describe the study. At enrollment, written informed consent will be obtained, and forms to release medical records will be signed. Randomization will occur in blocks of 16 via a sealed envelope with allocation (G-BMT vs. TAU).

Screening Procedures: Potential participants who contact the study coordinator will be screened for inclusion and exclusion criteria. The study coordinator will also call potential study participants who are identified by PCPs or on the BMT register. The study coordinator will administer a three part screener by phone or in person. For patients referred to the study by their PCP, the study coordinator will check records to confirm: receipt of BMT for ≥ 12 weeks and documentation of illicit opioid use in the prior 6 months. The study coordinator will elicit oral informed consent based on a standard script and then ask seven screening questions to confirm receipt of buprenorphine, ongoing illicit opioid use, interest in group treatment, pregnancy, and other study inclusion/exclusion criteria. We will not be conducting pregnancy tests. To screen for unstable mental health conditions, the research coordinator will administer the suicidality, PTSD/violence risk, and psychosis modules from the MINI 6.0. If criteria for any of these conditions are met or if the research coordinator expresses concerns about group suitability, [name] will make a clinical assessment in person prior to study enrollment.

Research Visits: The research assistant will meet with all participants at enrollment and at 2, 4, 6, 8, 12, and 16 weeks

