What if participants continue to abuse opioids during the G-BMT intervention? RCTs demonstrate that methadone maintenance is more effective than BMT for severe opioid addiction. In real life settings though, methadone maintenance may be unavailable or unacceptable to opioid users. G-BMT will provide an option for treatment intensification in primary care that currently does not exist. We will ensure safety of research participants by only recruiting patients who already receive BMT from a waived physician, closely supervising participants during the G-BMT intervention, and facilitating referral to methadone maintenance treatment programs if participants have 3 consecutive urine drug tests that are positive for opioids and they are willing to transfer their care. We will also use an independent data safety monitoring committee to review study outcomes and adverse events every six months of the RCT.

IV. Data and Safety Monitoring Plan

Detailed data and safety monitoring plan. Because this study includes an RCT, we will utilize an internal independent data safety monitoring committee (DSMC).

Protocol Summary: We will conduct a 16-week RCT in primary care to preliminarily test the G-BMT intervention (8 weekly group visits) for efficacy, acceptability, and feasibility in comparison to treatment as usual (TAU) among BMT patients with persistent opioid abuse. Eighty participants with persistent opioid abuse during office-based BMT will receive treatment intensification in the G-BMT intervention or through TAU (i.e. increased frequency of visits with their primary care provider, referral for counseling, and/or referral to addiction specialist). Research visits for data collection will occur at baseline, 2, 4, 6, 8, 12, and 16 weeks after randomization and will include computer-based interviews and urine drug testing. We will also collect electronic medical record data. We will test **efficacy** by collecting interview, urine, and medical record data examining *abstinence* (primary outcome), *retention in treatment*, and *HIV-risk behaviors*, including drug-related and sexually-related risk factors. We will test **acceptability** by assessing patient and provider satisfaction following the trial. We will test **feasibility** by examining process measures, such as *medication and visit adherence* and fidelity to the intervention manual.

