Einstein IRB for review and approval prior to implementation. Any protocol deviations will be reported to the Einstein IRB within 10 days on a standard IRB protocol deviation reporting form, and corrective action will be implemented as necessary. Reports to the data safety monitoring committee will occur every six months and will include information about any amendments to the protocol and any protocol deviations. Amendments to the protocol will be reported to the Program Officer at NIDA in annual progress reports.

Trial stopping rules: Interim analysis of the data will be conducted when 50% of the sample has accrued (N = 40). If the results show overwhelming, statistically significant differences in opioid abstinence or retention in treatment between the intervention and TAU arms, the study will be stopped. If we find that buprenorphine treatment discontinuation or serious adverse events are significantly more likely in the TAU arm compared to the G-BMT arm (e.g., if primary care providers stop buprenorphine treatment because of persistent opioid abuse), the randomized study will be halted. If the study is halted due to the results of an interim analysis, the study may still continue as a one-arm trial (e.g., all subjects will participate in the G-BMT intervention until 80 participants have enrolled) in order to collect additional process measures on conducting group visits.

Interim analyses will be conducted by [name] with close feedback from the biostatistician. The research team, in collaboration with the DSMC and the Program Officer of NIDA will review all pertinent data to determine whether to continue accrual. A decision to stop the study may be made at any time that the research team and DSMC agrees that an unacceptable type and/or frequency of adverse events has been observed. [name] will report the decision to terminate the study to the DSMC, IRB and NIDA within 48 hours of this determination. He will submit a narrative description of the reasons for early termination of the study to the IRB and NIDA within 10 days.

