Responsibility for data and safety monitoring: The Principal Investigator, [name], will be responsible for monitoring the safety and efficacy of this trial, executing the data and safety monitoring plan, and complying with the reporting requirements. The DSMC will vote on approval of the protocol prior to initiation of the RCT and submit meeting minutes to the IRB within 30 days. The DSMC will review safety and trial progress and provide advice with respect to study continuation, modification, and/or termination.

Frequency of DSM reviews: We will conduct continuous, close monitoring by study staff and investigators, with prompt identification and reporting of adverse events. Information about all unanticipated and serious adverse events will be reported as described above. The Principal Investigator will provide a summary of the data and safety monitoring report to the Program Officer at NIDA on an annual basis as part of the progress report. The DSMC will meet every 6 months and as needed in-person or via conference call.

Content of DSM report: [name] will provide a summary of study activities to the DSMC every 6 months. This will include the number of participants screened, enrolled, and lost to follow up; all adverse events; all pregnancies; and all protocol deviations.

The Principal Investigator will provide a summary of the data and safety monitoring report to the Program Officer at NIDA on an annual basis as part of the progress report. The data and safety monitoring report will include a brief description of the RCT, and a summary of baseline sociodemographic characteristics of participants enrolled to that point. The report will include a summary of the total number of participants screened, enrolled, and lost to follow up; and quality assurance or regulatory issues that have taken place in the past year; all actions or changes taken by the IRB with respect to the protocol; and all unanticipated adverse events (AEs) and Serious Adverse Events (SAEs). If applicable, the data safety and management report to NIDA will also include the results of any efficacy data analyses conducted.

DSM BOARD PLAN

Members and affiliation: We will establish a data and safety monitoring committee (DSMC) for the proposed study. This committee will include faculty members at the Albert Einstein College of Medicine who

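### The research team reviews by-arm interim results with no limit on access, so recruiting and outcome-collecting staff may learn them; the DSMC's itemised reports omit the outcomes promised to it.

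*Combined protocol and SAP*

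**What the plan says.** The interim look is set out under Trial stopping rules: "Interim analysis of the data will be conducted when 50% of the sample has accrued (N = 40"). It is comparative. One trigger for stopping is "overwhelming, statistically significant differences in opioid abstinence or retention in treatment between the intervention and TAU arms". Another is a significant excess of buprenorphine discontinuation or serious adverse events in the TAU arm. Interim analysis of efficacy data repeats both.

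On who does the work: "Interim analyses will be conducted by [name] with close feedback from the biostatistician". On who sees it: "The research team, in collaboration with the DSMC and the Program Officer of NIDA will review all pertinent data to determine whether to continue accrual". Responsibility for data and safety monitoring also makes the principal investigator answerable for monitoring efficacy as well as safety.

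On the committee, the section on continued opioid abuse during G-BMT says: "We will also use an independent data safety monitoring committee to review study outcomes and adverse events every six months of the RCT". Content of DSM report describes the six-monthly summary to the DSMC: "This will include the number of participants screened, enrolled, and lost to follow up; all adverse events; all pregnancies; and all protocol deviations". Frequency of meetings gives the same list, and Report of changes or amendments adds protocol amendments and deviations. None of the three names abstinence, retention or treatment discontinuation.

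**The concern.** The trial is open-label and single-site. If the people who recruit, track participants and collect urines know which arm is ahead, they may work harder, without intending to, to obtain follow-up in one arm. The primary outcome is sensitive to this because a missing urine is scored as opioid-positive (Main outcome variables, and again under Outcome Measures in the monitoring plan). The Power Analysis says the trial's more important purpose is an effect-size estimate for a larger trial, so a distorted estimate would carry forward even if no significance claim is made.

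The stopping trigger has no numerical boundary. The continuation decision is therefore a matter of judgement, and it matters who holds the data. The committee that is independent of the study should be the best-informed party, yet its itemised reports do not contain what the triggers require.

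**Working it through.** **1. The plan's own figures.** The interim fraction is 40/80 = 50%, as stated. The only power figure also reproduces. The design effect is 1 + (8 − 1) × 0.01 = 1.07, so the effective size is 40/1.07 = 37.4 per arm. With 10% in the control arm, 80% power and two-sided alpha 0.05 (assumed; none is stated), the detectable rate is 37.1%, against the plan's 37%. The present point does not depend on this figure or change it.

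**2. Who is on the research team.**
- Trial stopping rules: the team reviews the interim data and shares the decision on accrual.
- Recruitment: PCPs permit the team to contact patients.
- Collection of AEs and SAEs: team members carry out research visits and group visits.
- Nowhere: a closed report, a restricted list of recipients, or a statistician separate from these activities.

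The same term covers the reviewers and the people in contact with participants, and nothing separates them. It follows that these staff may see the comparison. It does not follow that they will.

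**3. What the DSMC receives.**
- Section on continued opioid abuse: outcomes and adverse events every six months.
- Trial stopping rules: a share in the interim review.
- Content of DSM report and Frequency of meetings: screening, enrolment and loss counts, adverse events, pregnancies, deviations.
- Report of changes or amendments: amendments and deviations.
- Content of DSM report, for NIDA: efficacy results, if any were analysed.

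Efficacy results are itemised for the funder's report but not for the DSMC's, although the DSMC is elsewhere said to review outcomes.

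**4. How many participants would be enrolled after the look.** Inputs: 80 participants in 12 months (Projected time table) and a primary outcome using week 8 and week 12 urines. Assumption: even accrual, 80/52 = 1.54 per week.
- The 40th participant enrols at 40/1.54 = week 26. Those with 12 weeks of follow-up by then enrolled by week 14: 14 × 1.54 = 21.5, about 22 of 40.
- Look done at N = 40 as written, or accrual paused: 80 − 40 = 40 remain (50%).
- Look waits for 12-week outcomes on all 40, no pause: week 26 + 12 = 38. Enrolled by then 38 × 80/52 = 58.5; remaining 80 − 58.5 = 21.5, about 22 (22/80 = 27.5%).
- A longer wait leaves fewer. With a 16-week lag, 42 × 80/52 = 64.6 are enrolled and about 15 remain. Such a lag is possible because Research Visits times visits from the start of G-BMT or TAU, and a group starts only once its block is filled.

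**5. Sensitivity of the primary outcome to one missed urine.** If abstinence requires both urines to be negative, one truly abstinent participant who misses a urine becomes a failure. In an arm of 40 that is 1/40 = 2.5 percentage points. At the assumed control rate of 10% (4 of 40), one such loss gives 3/40 = 7.5%. This shows the leverage of each missing urine. It is not an estimate of bias, because the documents give no basis for one.

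**The case against.** Several stronger readings are tempting, and the documents do not support them.

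- **That enrolling staff will know the result.** No section says the research assistant or study coordinator is shown it. The names of the person running the interim, the person making the pre-enrolment clinical assessment and the person resolving data discrepancies are removed from the public text, so they cannot be shown to be the same. Only possible knowledge is supported.
- **That the DSMC is denied outcomes, or receives reports not split by arm.** It is given outcomes in one section and a share in the interim review in another, and serious adverse events reach it within 48 hours. The report lists are not stated to be exhaustive, and silence about arms is not exclusion. What stands is a mismatch between sections.
- **That suitability screening biases the comparison.** The trigger "if the research coordinator expresses concerns about group suitability" leads to a clinical assessment before enrolment, and sealed-envelope randomisation follows consent. Knowledge at that stage could change who enters the trial, but it would affect both arms unless concealment failed.
- **That resolving discrepancies biases the data.** Urine results are entered separately by two staff and corrected against source documents, and participants enter interview answers directly. This route is weak.
- **That half the sample is always exposed.** That depends on when the look is done, as shown above.

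Equal visit schedules and equal payments in both arms also limit unequal follow-up, though they do not govern how hard staff pursue a missed visit. This is a developmental pilot that acknowledges it may be underpowered, and the DSMC and NIDA share the decision. These points lower the stakes. They do not supply an access rule.

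**Conclusion.** The point holds and the plan should be changed. By-arm interim results go to the research team with no restriction, and staff who recruit, follow up and collect outcomes may learn them while between about 22 and 40 of 80 participants remain to be enrolled. The upper figure needs the look at N = 40 or a pause in accrual. The lower one assumes even accrual over 12 months, no pause and a 12-week wait counted from enrolment; a longer wait gives fewer. The most credible route to bias is unequal follow-up effort combined with scoring missing urines as positive. Its size cannot be computed from the documents. The sections on what the DSMC receives conflict and must be reconciled. No sample size, power or alpha figure changes.

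**What to change.** Amend Trial stopping rules and Interim analysis of efficacy data. The single planned by-arm comparison should be prepared as a closed report by the biostatistician, or by another statistician with no part in recruitment or outcome collection, since the documents do not show how separate the biostatistician is from the team. It should go to the DSMC only, which returns a recommendation to continue, modify or stop. The research team should see pooled tabulations only. State whether the look is made when the 40th participant enrols or when those 40 have 12-week outcomes.

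Reconcile the section promising outcomes every six months with Content of DSM report, Frequency of meetings and Report of changes or amendments. List by-arm safety data (serious adverse events and buprenorphine discontinuation) in a six-monthly closed report, and confine by-arm abstinence to the planned interim. Putting abstinence in every report would add unplanned efficacy looks to a trial with no stated boundary.

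The cost is revised wording and closed reports, using the existing DSMC and biostatistician. The team loses early sight of tabulated by-arm results. The change blocks only the tabulated comparison: because the trial is open-label at one site, staff will still know individual participants' arms and results.

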Treatment as usual: Participants randomized to TAU will continue to receive BMT from their PCPs based on a standardized BMT intensification protocol. Prior to the study, PCPs at the CHC will receive one hour of training on BMT intensification. The protocol will require that all BMT patients with persistent opioid abuse receive at least monthly visits with urine drug tests collected at each visit. For participants randomized to TAU, PCPs will receive an automated e-mail reminder about the following protocol. After one urine drug test is positive for opioids, PCPs will increase the frequency of visits to twice monthly with referral for behavioral counseling. After two consecutive positive tests, PCPs will increase visit frequency to weekly. After three consecutive positive tests, PCPs will refer to an addiction specialist or opioid treatment program. We will measure frequency of BMT visits, referral for behavioral counseling and referral to opioid treatment programs during the study. We will determine *observed intensity* of BMT (defined below) for exploratory analyses of treatment outcomes.

Participant tracking: To facilitate tracking participants over the 16 week follow-up period we will use tracking procedures that we developed to retain drug users in our previous research studies, in which we have had an 85% retention rate over 6-month follow-up. On Locator Forms, we will record information about: 1) participants' address and phone number; 2) contact information of participants' family members, friends, case managers, physician, pharmacy, and drug treatment program; and 3) locations where participants hang out.

Data sources and measures: A complete list of measures is listed in Table 1.

Urine Drug Testing: Research visits will include urine drug test collection, which will be used for the primary outcome (both G-BMT and TAU participants will have an equal number of research visits and urines). Urine drug tests collected during G-BMT and TAU medical visits (*clinical drug tests*) will be used for secondary outcomes.

Testing will include opiates, oxycodone, buprenorphine, methadone, cocaine, and benzodiazepines.

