Provider Satisfaction: We will adapt a previously published questionnaire to assess acceptability of the intervention to participants' PCPs. Satisfaction will be measured in three areas: overall satisfaction with BMT, perceived effectiveness of BMT intensification and support for BMT at the CHC.¹⁰¹ We will add items for PCPs with patients randomized to the G-BMT intervention to assess satisfaction with communications with the G- BMT team and likelihood of referring patients to group-based BMT in the future.

Table 1. Timing and delivery of intervention and study measures

Measure	Study Instrument	Domain	Assessment Period (week)
Urine			
Opioid use	Observed urine	-	All [†]
Questionnaires			
Sociodemographic information	BHIVES Study ⁸²	-	0
HIV Risk Behaviors	AIDS risk inventory ⁹³	-	0, 8, 16
Self-reported drug use	Addiction Severity Index ⁹⁴	-	All
Depression	CES-D ⁹⁵	-	0, 8, 16
Self-efficacy	DTCQ-8 ⁹⁶	Self-efficacy	0, 8, 12, 16
Social Support	MSPSS ⁹⁷	Outcome Expectation	0, 8, 12, 16
Buprenorphine Knowledge	10 item questionnaire	Knowledge	0, 8, 16
Quality of Life	SF-12 ⁹⁸	-	0, 8, 16
Group cohesion*	GCQ-S ⁹⁹	-	2, 4, 8
Medical Records			
Medical Visits	-	-	1-16
Buprenorphine prescriptions	-	-	1-16
Referrals	-	-	1-16
Opioid use	Clinical urine		1-8
Retention in care	-	-	0, 12, 24
Intervention Materials			
Chronic Health Conditions	-	-	0
Self-assessment forms	Check-list	Goals	1-8
Intervention fidelity	Check-list	-	1-8
Post-intervention Questionnaires			
Patient satisfaction	PCBSS ¹⁰⁰	Barriers and Facilitators	8
Provider satisfaction	5 item questionnaire ¹⁰¹	-	8
Qualitative Interviews*	Interview Guide		8

*only collected for intervention arm; [†]Study visits (2,4,6,8,12,16 weeks) CES-D = Center for Epidemiologic Studies Depression Scale; DTCQ-8 = Drug-Taking Confidence Questionnaire, 8 item version; MSPSS = Multidimensional Scale of Perceived Social Support; SF-12 = SF-12 Health Survey; GCQ-S = Group Climate Questionnaire – Short Form; PCBSS = Primary Care Buprenorphine Satisfaction Scale

Analysis:

Main outcome variables:

Primary outcome (efficacy): we will use a dichotomous measure (yes/no) of *opioid abstinence* based on 30-day self-reported opioid use following completion of the intervention and the results of urine drug tests (opiates, methadone, oxycodone) at the 8 and 12 week research visits (see Figure 1). Missing urine drug tests will be considered to be positive for opioids.

Secondary outcomes (efficacy):

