Continuing BMT despite ongoing opioid abuse: Participants with three consecutive urine drug tests that are positive for opioids during group medical visits will be offered facilitated referral to methadone maintenance treatment program; however, some may refuse referral. In the G-BMT intervention arm, the research team will meet to discuss the risks and benefits of continuing BMT and participation in group medical visits. In the TAU arm, continuation of BMT will be up to the prescribing physician. If there is concern that risks of continuing treatment outweigh the potential benefits, the participant will be removed from the trial and referred to an

addiction specialist.

Burden of BMT intensification: We will collect data on adherence to medication and visits as a feasibility measure, and we will monitor treatment, after 50% of the sample has accrued.

Potential benefits for participants: Group visits have the potential to improve rates of opioid abstinence thereby reducing HIV risk behaviors and overdose risk. Our preliminary work on buprenorphine group visits has demonstrated that they are highly valued, therefore, other benefits, such as reductions in depressive symptoms or distress, may lead to improved health status.

Collection of AEs and SAEs: Because the research visits will include computerized interviews and urine collection, and the G-BMT intervention will include group counseling and buprenorphine education, participants are likely to incur no more than minimal risk of AEs. However, if AEs occur, they are likely to include psychological distress. AEs will be collected by members of the research team as they conduct research visits or group visits, and will be reported to [name] either immediately (for serious AEs) or during regular weekly project meetings (for non-serious AEs). Serious AEs could include death, life-threatening adverse reaction, inpatient hospitalization, persistent disability, or an event jeopardizing the participant's health.

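### A participant whose treatment risks are judged to outweigh benefits is removed from the trial, with no statement that research follow-up continues or that the participant is analysed as randomised

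*Combined protocol and SAP*

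**What the plan says.** The provision is in the combined protocol and SAP, Section IV, TRIAL SAFETY, in the risk-management paragraph on continuing BMT despite ongoing opioid abuse. It runs in four steps:

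- The trigger is worded for group visits: "Participants with three consecutive urine drug tests that are positive for opioids during group medical visits will be offered facilitated referral". The referral is for methadone treatment, and a participant may decline it.
- For G-BMT, the research team then weighs whether BMT and group attendance should go on.
- For usual care, the wording is different: "In the TAU arm, continuation of BMT will be up to the prescribing physician".
- The last step applies when treatment is judged to carry more risk than benefit. It names no arm and no decider, and its consequence is that "the participant will be removed from the trial and referred to an" (the referral is for specialist addiction care).

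Two other places cover the same situation without mentioning removal. For usual care, Section III (Treatment as usual) says: "After three consecutive positive tests, PCPs will refer to an addiction specialist or opioid treatment program". The Section III paragraph on continued opioid use during G-BMT makes methadone referral conditional on three consecutive positive tests and the participant's willingness.

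The primary outcome combines 30-day self-report with research urine tests at weeks 8 and 12. On missing results the plan states: "Missing urine drug tests will be considered to be positive for opioids". Neither analysis section (Section III, Analysis; Section IV, Data analysis plan) defines an analysis set or mentions removed participants. No section separates stopping treatment from leaving research follow-up.

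**The concern.** The removal sentence sits in a paragraph about persistent opioid use, which is what the primary outcome measures. Participants who reach it are likely to be doing badly on that outcome. If they leave the trial as well as the treatment, later data are missing for a reason related to outcome.

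The steps before the sentence also differ by arm. The three-test trigger is worded for group visits and leads to a research-team discussion in G-BMT. In usual care, continuation of BMT rests with the prescriber. Outcome-related loss that arises differently in two randomised arms can bias the comparison in either direction.

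The Power Analysis section says that estimating an effect size for a larger trial matters more than a significant result. Bias in the estimate would carry into that trial's design.

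**Working it through.** **1. Which data depend on staying in the trial** (Table 1; Main outcome variables; Medical records; Collection of AEs and SAEs)

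| Outcome | Source and timing | After removal |
|---|---|---|
| Abstinence (primary) | Self-report and research urines, weeks 8 and 12 | Missing urine counts as positive; denominator not stated |
| HIV risk behaviours | Interview, weeks 8 and 16 | Lost; no missing-data rule |
| Patient satisfaction | Questionnaire, week 8 | Lost if removal comes first; no rule |
| Adherence and retention | Medical records | Needs no research visit |
| Adverse events | Gathered by staff at research and group visits | No collection route described |

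Usual-care participants attend no group visits, so research visits are their only described route for adverse events.

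**2. The plan's own figure.** Inputs from the Power Analysis section: 40 per arm, control abstinence 10%, ICC 0.01, average group size 8, power 80%, detectable rate 37%. Alpha is not stated; two-sided 0.05 is assumed.

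- Design effect = 1 + (8 − 1) × 0.01 = 1.07, so effective n = 40/1.07 = 37.4 per arm.
- Mean rate = (0.10 + 0.37)/2 = 0.235.
- SE under no difference = √(2 × 0.235 × 0.765/37.4) = 0.0981.
- SE under the alternative = √((0.10 × 0.90 + 0.37 × 0.63)/37.4) = 0.0930.
- z = (0.27 − 1.96 × 0.0981)/0.0930 = 0.837, which gives power of 79.9%.

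Solving for 80% power gives 37.1%. The stated 37% reproduces, so no planning figure is in dispute.

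**3. If removed participants are dropped.** The documents give no removal rate. Assume r of 40 are removed from an arm, with r from 0 to 8, all non-abstinent. The arm's expected rate becomes 40p/(40 − r).

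| Dropped from TAU / G-BMT | TAU | G-BMT | Difference (points) |
|---|---|---|---|
| 0 / 0 | 4/40 = 10.0% | 14.8/40 = 37.0% | 27.0 |
| 0 / 4 | 10.0% | 14.8/36 = 41.1% | 31.1 |
| 0 / 8 | 10.0% | 14.8/32 = 46.25% | 36.3 |
| 4 / 4 | 4/36 = 11.1% | 41.1% | 30.0 |
| 8 / 0 | 4/32 = 12.5% | 37.0% | 24.5 |

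Even equal removal moves the difference, because the same count inflates the higher rate more.

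With no true difference, dropping 8 from one arm raises the nominal 5% rejection rate to about 6.5% when abstinence is 10% and about 12.4% when it is 37% (normal approximation, clustering ignored).

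**4. If removed participants stay in the denominator with missing urines positive.** When all of them are truly non-abstinent, the difference stays at 27.0 points and there is no bias. When each would have been abstinent with probability q, the arm loses r × q/40. For r = 8 this is 8 × 0.10/40 = 2 points at q = 10% and 8 × 0.50/40 = 10 points at q = 50%. Continued urine collection removes this second error as well.

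**The case against.** The strongest reply is that the primary outcome already has a rule. A removed participant without week 8 and 12 urines counts as positive, and no section says that such a participant is dropped. This stands as far as it goes: with all 80 randomised participants in the denominator, the figures in step 3 do not arise. The plan does not state that denominator, and the rule covers urine tests only.

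Four stronger readings are tempting, and the documents do not support them:

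- **Positive tests cause removal.** They do not. Three consecutive positives lead to an offer of referral and, in G-BMT, a discussion. Removal needs a separate judgement that risks outweigh benefits. The trigger also uses clinical urines, while the outcome uses research urines. Weekly testing in G-BMT therefore cannot be turned into a higher removal rate, and the plan gives no positivity or attendance figures for such an estimate.
- **Different people decide removal in each arm.** The removal sentence names no decider. The usual-care sentence concerns continuing BMT, which is not the same as trial membership. Only the process leading up to the sentence can be said to differ.
- **Adherence and retention are lost too.** Both come from medical records, under release forms signed at enrollment and with extraction six months later.
- **Harms would be hidden.** The Communication plan requires every serious adverse event to be reported, related or not. The weaker point remains: a duty to report does not supply a way to learn of events once study visits stop.

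**Conclusion.** The point holds as a fault in the follow-up and analysis rules. Read as written, a decision about treatment ends trial participation for people selected on something close to the primary outcome, and nothing keeps them in research visits or in the analysis. HIV-risk, satisfaction and adverse-event data are directly exposed. The abstinence comparison is exposed only if removed participants are dropped, which the plan neither states nor rules out.

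On the assumption of 0 to 8 of 40 removed from one arm, all non-abstinent and all dropped, the 27-point planning contrast would lie between 24.5 and 36.3 points. This is a range under assumption and does not predict what will happen: the actual number, arm and direction are unknown. A correction is worthwhile because the trial exists mainly to supply an effect estimate and the repair is small.

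**What to change.** Replace the removal wording with a statement that, whatever the treatment or referral decision, the participant:

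- stays in research visits, medical-record extraction and AE/SAE collection unless consent is withdrawn; and
- is analysed in the randomised arm, with missing urines counted as positive.

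Carry the same statement into both analysis sections and the consent form. Report treatment discontinuations and withdrawals from research by arm, with reasons. Since the outcome urine panel includes methadone and referral may be to a methadone programme, also state how prescribed methadone is scored.

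The Treatment as usual section, the Section III paragraph on continued use during G-BMT and the TRIAL SAFETY paragraph should be reconciled on what follows three consecutive positive tests in each arm. No clinical rule is proposed here.

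Research visits are already separate from clinical visits, so no new procedure is needed. The downside is staff time and compensation for the remaining visits: at most 6 × 25 dollars = 150 dollars per participant.
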